8.1.1.1. Self-controlled Risk Interval Design (Primary Study Design for Acute Events)

The SCRI design will compare the risk of the AESIs in a postvaccination risk window to a postvaccination control window within the same individual, in a cohort of individuals vaccinated with Ad26.COV2.S (Figure 1). The use of a postvaccination control window (rather than a prevaccination control window) avoids bias due to healthy user vaccinee effect. To account for the possibility that increased risks of AESIs might extend beyond the risk interval, the risk and control windows may be separated by buffer periods for events that do not have well established risk intervals in the literature (to be defined in the statistical analysis plan [SAP]).

[figure not shown]

Figure 1: Self-Controlled Risk Interval Design

8.1.1.2. Cohort Design With Concurrent Active Comparator (Primary Study Design for Non-acute Events and Sensitivity Analysis for Acute Events)

[figure not shown]
For the cohort design, the incidence of AESIs will be compared between the 1-dose Ad26.COV2.S exposed cohort and the 2-dose BNT162b2 comparator cohort (Figure 2):

- **Exposed cohort**: individuals will have received at least 1 dose of Ad26.COV2.S administered according to US recommendations (BLA approval or EUA). The reference date will be the first date of receipt of Ad26.COV2.S.
- Active comparator cohort: individuals will have been vaccinated with at least 1 dose of the primary series of BNT162b2 at any time on or after the start of the study observation period. The reference date of the comparator cohort will be the calendar date of the first dose in the primary series of BNT162b2. Individuals will be matched by propensity scores (PS) and calendar time (within 2 weeks) at the reference date using a 1:4 ratio of exposed to comparator within the Data Partner distributed database, if feasible; the matching ratio will be dependent on the findings of the relative uptake of vaccinations identified during feasibility assessments and monitoring.

COVID-19 vaccines were first administered to priority populations at high risk of severe disease or exposure, including older adults or those with comorbidities. Therefore, information on the presence of comorbidities within 1 year prior to the reference date and older age will be collected and included in the PS models. The covariates for the propensity score models, to be assessed up to the reference date, are described in Section 8.7.2.1.

[figure not shown]
Cohorts will be defined utilizing existing secondary healthcare data sources. One year of medical and pharmacy insurance enrollment prior to the reference date will be required to determine whether individuals meet the study criteria and to define baseline characteristics. Data on the occurrence of AESI will be extracted within the 1 year after the reference date.

Figure 2: Cohort Study Design

[figure not shown]
Ad26.COV2.S exposed cohort

Outcome-specific follow-up periods after vaccine receipt

Comparator BNT162b2 exposed cohort

Outcome-specific risk periods after dose 1 for outcomes with risk windows \leq 21 days

Comparator BNT162b2 exposed cohort

If vaccine dose 2 is received during the outcome-specific risk period after dose 1, the risk periods of dose 1 and dose 2 are concatenated into a single risk period, and follow-up ends after the duration of the outcome-specific risk period following dose 2. If vaccine dose 2 is not received, the outcome-specific risk window extends the full length from dose 1.

Outcome-specific risk windows:

- 2 days: anaphylaxis.
- 14 days: generalized convulsion, arrhythmia, acute kidney failure, acute hepatic failure.
- 21 days: cardiac inflammatory disorders, including myocarditis and pericarditis, and sensorineural hearing loss.

- 28 days: microangiopathy, disseminated intravascular coagulation, DVT, pulmonary embolism, hemorrhagic and non-hemorrhagic stroke, acute myocardial infarction, coronary artery disease (including acute myocardial infarction), heart failure, stress cardiomyopathy, venous thrombosis composite endpoint, arterial thrombosis composite endpoint, stroke composite endpoint.
- 42 days: encephalitis (including acute demyelinating encephalomyopathy and meningoencephalitis), Guillain Barré Syndrome, Bell's palsy, immune thrombocytopenia, thrombocytopenia, transverse myelitis.
- 365 days: autoimmune thyroiditis, acute aseptic arthritis, multiple sclerosis (including optic neuritis), Type 1 diabetes mellitus.

Note that follow-up time for the primary analysis will end upon receipt of a booster dose of Ad26.COV2.S or a booster dose of any COVID-19 vaccine.

8.1.2. Rationale for Study Design

The AESIs included in this study are considered as potential safety risks following administration of Ad26.COV2.S. The selected AESIs represent a heterogeneous group including multiple organ systems, and acute and chronic conditions (Section 8.3.4).

The SCRI design has been selected as the primary design for acute events (ie, AESIs expected to occur within a disease risk period of 60 days) because it only includes vaccinated individuals, which avoids misclassification of unexposed status due to incomplete capture of vaccinations in health insurance claims databases. Because it uses each individual as its own control, the SCRI design avoids potential confounding by factors that do not vary with time. To account for the possibility that increased risks of AESIs might extend beyond the risk interval, the risk and control periods may be separated by buffer periods for events that do not have well established risk intervals in the literature (to be defined in the SAP). Although most AESIs are age-dependent, an age bias is not anticipated because the follow-up period is short compared with the age effect on the incidence of AESIs. However, because the SCRI design generally has less statistical power and for some AESIs, may be subject to confounding by other time-invariant confounders such as seasonality (a proxy for respiratory infections), a cohort design with an active comparator (BNT162b2 exposed) will be used in sensitivity analyses of acute events.

Because the SCRI design is not appropriate for non-acute events, the cohort design with an active comparator (BNT162b2 exposed) will be used to assess these types of events (ie, AESIs expected to occur within a disease risk period of more than 60 days; see Table 1). BNT162b2 has been selected as the active comparator because it is the most commonly used COVID-19 vaccine in the US, and as such should be representative of COVID-19 vaccinees and provide sufficient numbers for all comparisons.

Disease-specific risk periods have been defined for all AESIs, regardless of acute or non-acute; however, these risk periods are based on currently available evidence (eg, from experience with other marketed vaccines or knowledge of COVID-19) and may not be strictly applicable to the Ad26.COV2.S vaccine (Table 1). For this reason, alternative risk periods will be considered in sensitivity analyses for outcomes that do not have a well-defined risk periods (to be defined in the SAP).

8.1.3. Feasibility Assessment (Monitoring Phase)

A feasibility assessment, including monitoring of vaccine uptake, will be conducted for each participating data source to confirm the feasibility of implementing the planned final analysis in the available data sources. The monitoring phase will start after the launch date of Ad26.COV2.S in the US (27 February 2021). Participating data sources will be consulted on a regular basis (depending on data update schedules) from Ad26.COV2.S vaccination launch and over a period of at least 18 months.

The monitoring phase will include the following objectives:

- To assess vaccine utilization among the Ad26.COV2.S and mRNA COVID-19 vaccine—exposed populations across different geographical areas and to identify confounding factors that will be used as PS modeling covariates in the cohort design. Potential confounding factors to be described in monitoring analyses (where available) are age, overall healthcare utilization, preventive healthcare utilization, medication utilization, race/ethnicity, and presence of comorbidities.
- To survey the Data Partners to assess possible linkage to vaccine registries in different US states and assess, if possible, based on ongoing linkage activities between Departments of Public Health and Data Partners, potential under-reporting of exposure.
- To monitor the number of AESIs in individuals exposed to Ad26.COV2.S and mRNA COVID-19 vaccines in the available data resources.

8.2. Setting and Study Population

8.2.1. Study Setting

This study will be conducted using health plan claims data held by 4 large national insurers that participate in the FDA's Sentinel System, including CVS Health (Aetna), HealthCore (Anthem), Humana, and Optum. Further information on the data sources used in this study can be found in Section 8.4. The study period will begin on 27 February 2021, the day Ad26.COV2.S was authorized for emergency use in the US, although data from before 27 February 2021 will be used to define patient characteristics and vaccine history.

8.2.2. Population Selection Criteria

8.2.2.1. Inclusion/Exclusion Criteria for the Self-Controlled Risk Interval Design

For analyses of acute outcomes, individuals will be included in SCRI analyses if the following criteria are met. Note that the eligibility criteria will be applied separately for analysis of each AESI (Additional details regarding requirements for follow-up during the risk and control windows will be defined in the SAP):

- Received a dose of Ad26.COV2.S vaccine during the study period as their first dose of any COVID-19 vaccine
- Experienced the AESI during a risk period (as defined in Table 1) or control period (to be defined in the SAP)

- Did not experience the specific AESI during the pre-event washout period (as defined in Table 1)
- Have at least 1 year of continuous health plan enrollment with medical and prescription drug coverage prior to the reference date and an earliest coverage date on or before 11 December 2020 (to maximize the ability to identify the first COVID-19 vaccine administered during the study period)
- Aged 18 years or older at the reference date

8.2.2.2. Criteria for Exposed and Active Comparator Cohorts

The inclusion and exclusion criteria for each cohort are listed in the subsections below. For both the exposed (Ad26.COV.2.S) and comparator (BNT162b2) cohorts, individuals will be identified at their first observed COVID-19 vaccine dose during the study period, with the date of the dose being the reference date.

While at least 1 year of enrollment in the data plan before the reference date will be required for individuals to be included in the study, if greater than 1 year of baseline data are available for individuals, all available baseline data will be used to define outcome-specific washout periods for some chronic conditions, such as Type 1 diabetes.

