- composite endpoints within 1-28 days in individuals vaccinated with the Ad26.COV2.S vaccine and in corresponding individuals vaccinated with the BNT162b2 vaccine or during a control window within the same individual
 - o venous thrombosis, including PE and DVT
 - o arterial thrombosis, including coronary artery disease and non-hemorrhagic stroke
 - o stroke, including non-hemorrhagic and hemorrhagic strokes
- the incidence of encephalitis (including acute demyelinating encephalomyelopathy and meningoencephalitis), Guillain Barré Syndrome, Bell's palsy, immune thrombocytopenia, thrombocytopenia, and transverse myelitis within 1-42 days in individuals vaccinated with the Ad26.COV2.S vaccine and in corresponding individuals vaccinated with the BNT162b2 vaccine, or during a control window within the same individual.
- the incidence of autoimmune thyroiditis, acute aseptic arthritis, multiple sclerosis (including optic neuritis), and Type 1 diabetes mellitus **within 1-365 days** in individuals vaccinated with the Ad26.COV2.S vaccine and in corresponding individuals vaccinated with the BNT162b2 vaccine.

Secondary Objective

• The secondary objective for this study is to describe the number of individuals who received a second dose of Ad26.COV2.S as well as their baseline demographic characteristics.

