- Administration of certain vaccines, such as influenza vaccine, any pneumococcal vaccine, any shingles vaccine, or any human papillomavirus (HPV) vaccine during the year before the reference date (for active comparator design) or from 90 days before the reference date and during the risk and control windows (for SCRI design)
- Other vaccinations received concurrently with the Ad26.COV2.S vaccine or BNT162b2 vaccine
- Indicator variables for previous occurrence of each AESI using all available history before reference date (Table 1).

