8.3.4.2. Risk Windows

Status: Approved, Date: 20 October 2022

Table 1: AESI-Specific Risk Windows and Background Incidence Rates

Body system	AESI	Disease-specific washout period before administration of Ad26.COV2.S or BNT162b2 for active comparator design	Disease- specific washout period before event for SCRI design	Disease- specific risk period following the administration of Ad26.COV2.S or BNT162b2	Range of adult background rates per 100,000 person- years reported in the external literature ^{a,b}
Nervous and central nervous system	Encephalitis, including ADEM & meningoencephalitis	180 days	180 days	1-42 days	2-73 (Li X et al. 2021; Baker MA et al. 2013; Ostropolets A et al. 2022; Esposito D et al. 2018)
	Guillain-Barré Syndrome	365 days	365 days	1-42 days	< 1-23 (Baker MA et al. 2013; Li X et al. 2021; Klein NP et al. 2010; Ostropolets A et al. 2022; Esposito D et al. 2018)
	Transverse myelitis	365 days	365 days	1-42 days	< 1-5 (Baker MA et al. 2013; Li X et al. 2021; Klein NP et al. 2010; Ostropolets A et al. 2022)
	Bell's palsy	180 days	180 days	1-42 days	40-174 (Li X et al. 2021; Baker MA et al. 2013; Ostropolets A et al. 2022)
	Multiple sclerosis, including optic neuritis	All available	Not applicable for SCRI	1-365 days	2-29 (Alonso A and Hernán MA 2008; Klein NP et al. 2010; Esposito D et al. 2018)
	Sensorineural Hearing loss	365 days	365 days	1-21 days	12-81 (Alexander TH and Harris JP 2013)
	Generalized convulsions (without epilepsy)	180 days	180 days	1-14 days	25-120 (Kotsopoulos I et al. 2005)
	Generalized convulsions (with epilepsy)	365 days	365 days	1-14 days	14-62 (Kotsopoulos I et al. 2005)

CONFIDENTIAL – FOIA Exemptions Apply in U.S.

Body system	AESI	Disease-specific washout period before administration of Ad26.COV2.S or BNT162b2 for active comparator design	Disease- specific washout period before event for SCRI design	Disease- specific risk period following the administration of Ad26.COV2.S or BNT162b2	Range of adult background rates per 100,000 person- years reported in the external literature ^{a,b}
Immune system	Autoimmune thyroiditis	All available	Not applicable for SCRI	1-365 days	5-97 (Klein NP et al. 2010; Esposito D et al. 2018)
	Immune thrombocytopenia	365 days	365 days	1-42 days	1-56 (Baker MA et al. 2013; Klein NP et al. 2010; Li X et al. 2021; Ostropolets A et al. 2022; Esposito D et al. 2018)
	Thrombocytopenia	90 days	90 days	1-42 days	

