	Type 1 diabetes mellitus	All available	Not applicable for SCRI	1-365 days	19-382 (Klein NP et al. 2010; Baker MA et al. 2013; Esposito D et al. 2018)
	Acute aseptic arthritis ^c	All available	Not applicable for SCRI	1-365 days	3-205 (Pennisi M et al. 2019; Esposito D et al. 2018)
	Anaphylaxis	180 days	180 days	0-2 days	7-85 (Lee S et al. 2017; Baker MA et al. 2013; Li X et al. 2021; Ostropolets A et al. 2022; Esposito D et al. 2018)
	Composite endpoint – Cardiac inflammatory disorders, including myocarditis and pericarditis	365 days	365 days	1-21 days	2-54 (Li X et al. 2021; Baker MA et al. 2013; Ostropolets A et al. 2022)
	Microangiopathy	365 days	365 days	1-28 days	
	Heart failure	All available	All available	1-28 days	812-5,020 (Cuthbertson CC et al. 2018) ^d
	Stress cardiomyopathy	365 days	365 days	1-28 days	
	Coronary artery disease, including acute myocardial infarction	All available	All available	1-28 days	41-823 (Manemann 2015)
	Acute myocardial infarction	180 days	180 days	1-28 days	6-1,514 (Li X et al. 2021; Ostropolets A et al. 2022)
	Arrhythmia	All available	All available	1-14 days	9-6,195 (Kjerpeseth LJ et al. 2021) ^e

CONFIDENTIAL – FOIA Exemptions Apply in U.S. Status: Approved, Date: 20 October 2022

Body system	AESI	Disease-specific washout period before administration of Ad26.COV2.S or BNT162b2 for active comparator design	Disease- specific washout period before event for SCRI design	Disease- specific risk period following the administration of Ad26.COV2.S or BNT162b2	Range of adult background rates per 100,000 person- years reported in the external literature ^{a,b}
Blood and lymphatic system	Deep vein thrombosis	180 days	180 days	1-28 days	66-1,206 (Li X et al. 2021; Huang W et al. 2014; Ostropolets A et al. 2022)
disorders	Pulmonary embolism	180 days	180 days	1-28 days	20-427 (Li X et al. 2021; Huang W et al. 2014; Ostropolets A et al. 2022)
	Disseminated intravascular coagulation	180 days	180 days	1-28 days	< 1-203 (Li X et al. 2021; Singh B et al. 2013; Ostropolets A et al. 2022)
	Non-hemorrhagic stroke	180 days	180 days	1-28 days	17-1,523 (Li X et al. 2021; Feigin VL et al. 2015; Ostropolets A et al. 2022)
	Hemorrhagic Stroke	180 days	180 days	1-28 days	13-506 (Li X et al. 2021; Feigin VL et al. 2015; Ostropolets A et al. 2022)
	Cerebral venous thrombosis	180 days	180 days	1-28 days	< 1-1.7 (Coutinho JM et al. 2012)
	Peripheral arterial thrombosis	180 days	180 days	1-28 days	, , , , , , , , , , , , , , , , , , ,

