8.4. Data Sources

This study will be conducted using health plan claims data held by Data Partners that participate in the FDA's Sentinel System, including CVS Health (Aetna), HealthCore (Anthem), Humana, and Optum. These Data Partners typically update their quality-checked data 3 to 4 times per year, although some are updating more frequently with fresher data (ie, shortened data lags) to support FDA-initiated COVID-19 analyses. The study will use the most up-to-date standardized and curated data source available within each Data Partners, leveraging the Sentinel Common Data Model (SCDM). These databases capture longitudinal information on vaccines, medical products (dispensed prescriptions, vaccines administered), inpatient and outpatient diagnoses, inpatient and outpatient treatments and procedures, based on billing codes as well as laboratory results.

The average enrollment length for patients across data sources participating in the Sentinel System is similar to other claims databases of members with medical and pharmacy coverage; about 25% of patients have over 3 years of enrollment, and patients with chronic conditions such as diabetes and older members typically have longer than average enrollment periods within these databases. All study data will be accessed with procedures compliant with US subject confidentiality requirements, including the Health Insurance Portability and Accountability Act of 1996 (HIPAA). Where appropriate, as required by local regulations, this study will be undertaken only after the IEC/IRB has given full approval of the final protocol, any applicable amendments, and the sponsor has received a copy of this approval.

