8.7.2. Main Statistical Methods

8.7.2.1. Propensity Score Matching

For the cohort designs, matching on calendar time at vaccination (within 2 weeks) and PS will be used to ensure comparability between individuals exposed to Ad26.COV2.S versus BNT162b2. The PS is the predicted probability of an individual being classified in the exposed cohort versus the comparator cohort, given a set of observed covariates. Propensity scores will be estimated with multivariable logistic regression models with Ad26.COV2.S exposure as the dependent variable and baseline covariates as the independent variables. The baseline covariates used to fit the PS model will be the individual characteristics described in Section 8.3.2 and indicators for occurrence of AESI in the disease-washout period described in Section 8.3.4.2.

This large-scale empirical adjustment strategy should address expected confounders that are recorded in the databases, including demographics and comorbidities associated with AESIs. The study will be subject to the limitation that some confounders may be unmeasured or inadequately represented in claims data, including lifestyle behaviors, such as diet and exercise.

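### Washout length for the four one-year outcomes varies from person to person, and the protocol neither balances it between the matched arms nor checks that it is balanced

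*Protocol*

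**What the plan says.** Section 7 lists, for the 1-365 day window, "the incidence of autoimmune thyroiditis, acute aseptic arthritis, multiple sclerosis (including optic neuritis), and Type 1 diabetes mellitus". Table 1 (Section 8.3.4.2) marks these four as not applicable for the self-controlled design and gives each a washout of all available history. Section 8.2.2.2 sets a floor of one year of enrollment and adds that, where more exists, "all available baseline data will be used to define outcome-specific washout periods for some chronic conditions, such as Type 1 diabetes". Section 8.2.2.2.3 removes anyone with the diagnosis in the washout from that outcome's analysis.

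On how long people are observed, Section 8.4 states: "about 25% of patients have over 3 years of enrollment, and patients with chronic conditions such as diabetes and older members typically have longer" enrollment than average. Section 8.4.2 says one database can be traced back to January 2006.

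On adjustment, Section 8.7.2.1 states: "The baseline covariates used to fit the PS model will be the individual characteristics described in Section 8.3.2", together with indicators for outcomes in the washout period. Section 8.3.2 lists demographics, pregnancy, frailty, one-year medical history, utilization, medication, COVID-19 history, vaccinations and prior-outcome indicators. It does not list length of enrollment. Matching uses the PS and calendar time within two weeks, inside each Data Partner (Section 8.1.1.2). Section 8.7.2.2 assesses balance of characteristics by absolute standardized differences.

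**The concern.** In claims data, a chronic disease counts as incident when no earlier code is found. The chance that an established case shows no earlier code falls as the searchable history lengthens. Length of lookback therefore governs how many prevalent cases leak into the outcome, and under this rule it ranges from one year to possibly many.

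Unequal lookback between people does no harm to a null comparison if its distribution is the same in both arms. If the distributions differ after matching, the false-incident rate differs too, and the difference appears in the IRR as a vaccine effect or as protection. A larger sample does not shrink it. Because enrollment length is not a listed characteristic, the planned balance table would not show the imbalance. The estimates at stake are the only primary estimates for these four outcomes.

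**Working it through.** **The plan's own figure.** The protocol gives no figure for lookback by arm. Its only precision basis for the cohort is Table 3. For 100,000 versus 400,000 people, 60 days, 50 per 100,000 person-years and a true relative risk of 1.0, expected events are a = 100,000 × (60/365) × 50/100,000 = 8.22 and b = 4 × 8.22 = 32.88. SE = √(1/8.22 + 1/32.88) = 0.390. The probability that the upper bound is below 3.0 is Φ(ln 3/0.390 − 1.96) = 0.804, against 0.805 stated. It reproduces.

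**Illustration 1.** All inputs except the true rate are assumptions. Rate in an arm = I + (1 − p)·F1 + p·F3. I is the true rate: 19 or 382 per 100,000 person-years, the ends of Table 1's range for Type 1 diabetes. p is the share with more than three years of lookback. F1 and F3 are the false-incident rates with up to, and with more than, three years. The true IRR is 1.0. The shorter lookback is placed, arbitrarily, in the exposed arm.

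| I | F1/F3 | Exposed, p = 0.15 | Comparator, p = 0.25 | IRR | Comparator, p = 0.40 | IRR |
|---|---|---|---|---|---|---|
| 19 | 20/5 | 36.75 | 35.25 | 1.04 | 33 | 1.11 |
| 19 | 60/20 | 73 | 69 | 1.06 | 63 | 1.16 |
| 19 | 100/30 | 108.5 | 101.5 | 1.07 | 91 | 1.19 |
| 382 | 20/5 | 399.75 | 398.25 | 1.00 | 396 | 1.01 |
| 382 | 60/20 | 436 | 432 | 1.01 | 426 | 1.02 |
| 382 | 100/30 | 471.5 | 464.5 | 1.02 | 454 | 1.04 |

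Example, second row: 19 + 0.85 × 60 + 0.15 × 20 = 73; 19 + 0.75 × 60 + 0.25 × 20 = 69; 73/69 = 1.06.

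**Illustration 2.** Here the false-incident rate is built from prevalence. Rate = I + 0.9·P·[s·m3 + (1 − s)·m1]. P is prevalent disease (200 to 1,000 per 100,000). m1 and m3 are the shares of prevalent cases left uncoded with short and long lookback (10% and 2%, or 5% and 1%). 0.9 is the share of those then coded in follow-up. s is the share with more than three years. All are assumed.

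- s = 15% versus 25%: IRR 1.03 to 1.08 at I = 19, and 1.00 to 1.02 at I = 382.
- s = 10% versus 30%: IRR 1.06 to 1.17 at I = 19, and 1.00 to 1.03 at I = 382. The top value at 19 is (19 + 900 × 0.092)/(19 + 900 × 0.076) = 101.8/87.4 = 1.165.
- s = 25% in both arms: IRR 1.00 throughout.

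**Together.** The spurious IRR runs from about 1.03 to 1.19 at the lowest Type 1 diabetes rate and from about 1.00 to 1.04 at the highest. If the comparator has the shorter lookback, each ratio inverts; 1.19 becomes 91/108.5 = 0.84.

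**Against random error.** Suppose 100,000 and 400,000 people are each followed for the full 365 days. The 95% interval factor exp(1.96·√(1/a + 1/b)) is then 1.65 at 19 per 100,000 (19 and 76 events) and 1.12 at 382 (382 and 1,528 events). False-incident cases also count as events, so the interval at the low rate would be narrower. With 73 and 4 × 69 = 276 events the factor is 1.29.

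**The case against.** The strongest reply is that the needed premise is missing. Bias requires a difference in lookback between matched arms, and nothing in the protocol shows one. A reader might infer that Ad26.COV2.S recipients have shorter enrollment and that these outcomes will be inflated in that arm. The documents do not support that. Both arms are vaccinees of the same insurers under the same enrollment floor, and they are matched within Data Partner and within two weeks. The 25% figure describes patients across the Sentinel data sources, not either arm, and not a cohort already restricted to at least one year. This part of the objection stands: size and direction are unknown.

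Much of any difference may already be removed. Within-partner matching takes out differences in database start dates, and age, comorbidity, utilization and drug classes are in the PS. That also stands, but in part only, because these are correlates of plan tenure and the medical history is measured over one year. Case validation and quantitative bias analysis (Section 8.3.4.1) could catch false-incident cases. They are optional, however, and do not equalize lookback.

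It may be said that one more covariate is a matter for the SAP. The lists in Section 8.3.2 are partly open, but the openness lies inside named categories, none of which covers enrollment length. Section 8.7.2.1 fixes the PS covariates by reference to that list. The point concerns a variable washout paired with a covariate set that leaves out its length.

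A reader might also infer that the prior-outcome indicators in the PS are flawed in the same way. For an outcome's own indicator this fails: people with a recorded prior occurrence are excluded from that outcome's analysis, so the indicator is constant among those analysed. No effect through the indicators for other outcomes is shown.

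**Conclusion.** The concern holds as a conditional one. The protocol uses a washout of person-specific length for four primary outcomes and does not adjust for, match on or check that length. If the matched arms differ in it, the IRR is biased; if they do not, no spurious effect arises from this source. The illustrated bias is about 1.03 to 1.19 at 19 per 100,000 person-years and about 1.00 to 1.04 at 382, or the inverse. These figures rest on assumed false-incident rates, prevalence and arm splits, and on follow-up of about one year per person. They are not estimates for this study. They apply the Type 1 diabetes range only; the other three outcomes would need their own assumed leakage rates. In a single analysis a bias of this size would mostly lie within random error. It is still systematic, greatest for rare outcomes, and cheap to prevent. Using all available history is not itself an error.

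**What to change.** Keep the all-available washout. Add length of continuous enrollment before the reference date, for example 1 to under 2, 2 to under 3, and 3 or more years, to the Section 8.3.2 covariates and so to the PS model. Report its distribution by arm and its standardized difference before and after matching.

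The cost is one covariate. Each Data Partner already reads enrollment dates to apply the one-year and 11 December 2020 criteria, and no loss of sample is expected beyond ordinary matching. Balancing lookback makes the leakage equal between arms but does not remove it, so false-incident cases common to both arms would still pull a real effect toward 1.
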